3.1. Efficacy Assessments

3.1.1. Seizure Frequency and Type (eDiary)

Subjects will record details regarding their seizures (frequency and type) in an eDiary. Any BZD use will also be recorded in the diary. Seizure frequency and type will be assessed based on information recorded by the subject in the eDiary.

Seizure frequency is defined as the total number of focal onset seizures over the analysis period of interest divided by the total number of days with no missing seizure counts in the corresponding period multiplied by 7. For cluster seizures, which are a group of seizures too numerous to count, the number of cluster episodes will be included as one seizure event. Unless otherwise specified, Seizure frequency will only be calculated for focal onset seizures, which include focal aware seizures without motor signs, focal aware seizures with motor signs, focal impaired awareness seizures and focal to bilateral tonic-clonic seizures.

3.1.2. Patient's Global Impression of Change

The self-report measure Patient's Global Impression of Change (PGIC) reflects a patient's belief about the efficacy of treatment. It is a 7-point scale depicting a patient's rating of overall improvement. Patients rate their change as "very much improved," "much improved," "minimally improved," "no change," "minimally worse," "much worse," or "very much worse."

3.1.3. Clinical Global Impression-Severity of Symptoms Scale

The CGI-S is an observer-rated scale that will be used to measure symptom severity. It is important to note that the observer or rater will provide their assessment of the subject's symptoms at the time of the current visit.

To perform this assessment, the investigator (or designee) will answer the following question: "Considering your total clinical experience with this particular population, how ill is the subject at this time?" Response choices are 0 = not assessed; 1 = normal, not at all ill; 2 = borderline ill; 3 = mildly ill; 4 = moderately ill; 5 = markedly ill; 6 = severely ill; and 7 = among the most extremely ill subjects.

3.1.4. Clinical Global Impression-Improvement Scale

The CGI-I is an observer-rated scale that will be used to measure the subject's symptom severity compared with before initiation of treatment with IMP. It is important to note that the observer or rater will provide their assessment of the subject's current level of symptoms compared with their symptoms at baseline (Visit 1).

The investigator (or designee) will rate the subject's change from baseline in symptom severity (as related to seizure frequency and severity) using the following response choices: 0 = not assessed, 1 = very much improved, 2 = much improved, 3 = minimally improved, 4 = no change, 5 = minimally worse, 6 = much worse, and 7 = very much worse.

3.1.5. Quality of Life in Epilepsy – 31

The Quality of Life in Epilepsy – 31 (QOLIE-31) was developed in cooperation with professional postgraduate services, a division of Physicians World Communications Group and the QOLIE Development Group. The 31-item QOLIE-31 (Version 1.0) has been derived from the longer QOLIE-89 (Rausch & Crandall, 1982; Cramer et al, 1998).

The QOLIE-31 contains 7 multi-item scales that tap the following health concepts: emotional well-being, social functioning, energy/fatigue, cognitive functioning, seizure worry, medication effects, and overall quality of life. A QOLIE-31 overall score is obtained using a weighted average of the multi-item scale scores. The QOLIE-31 also includes a single item that assessed overall health.

Details of QOLIE-31 categories are provided in Section 9.2.

3.1.6. Health Utilities Index

The Health Utilities Index (HUI) is a rating scale used to measure general health status and health-related quality of life. The HUI questionnaires are designed to map onto 2 classification systems, HUI-2 and HUI-3, capable of measuring 24,000 and 972,000 unique health states, respectively. The HUI classifications measure a range of health domains with examples including sensation, mobility, pain, cognition, ambulation, and emotion (Horsman et al, 2003).

Details of HUI categories are provided in Section 9.3.

3.2. Safety Assessments

3.2.1. Adverse Event (AE)

An adverse event is any untoward medical occurrence in a patient or clinical trial subject, temporally associated with the use of trial treatment, whether or not considered related to the trial treatment. An AE can therefore be any unfavorable and unintended sign (including an abnormal laboratory finding), symptom, or disease (new or exacerbated) temporally associated with the use of trial treatment. All adverse events will be recorded on the ADVERSE EVENTS eCRF.

Adverse events with missing severity will have the severity imputed as 'Severe' for the AE tabulations. Adverse events with missing relationship to IMP will have the relationship imputed as 'Related' for the AE tabulations if the AE started on or after the first dose of IMP. However, in the data listings these missing severity and/or relationship will be presented as missing.

3.2.1.1. Treatment-emergent Adverse Event (TEAE)

Any event reported on the eCRF that occurs on or after the initiation of IMP through the last follow up contact is considered treatment emergent. Additionally, it is assumed that an Adverse Event which was reported to have started on Day 1 without an associated onset time is assumed to be treatment emergent.

3.2.1.2. Serious Adverse Event (SAE)

Adverse events that meet the definition of SAE in the protocol will be captured in the ADVERSE EVENTS eCRF.

3.2.1.3. Adverse Events of Special Interest

Adverse events of special interest (AESI) will be captured and monitored during this study. AESI include Adverse Events Potentially Related to Abuse or Dependence, Hematologic Abnormalities and Abnormal Liver Function Tests as defined in the protocol. These events will be noted by the investigator in the ADVERSE EVENTS eCRF.

3.2.2. Clinical Safety Laboratory Assessments

The clinical laboratory tests as listed in the protocol will be performed in accordance with the laboratory manual and the Schedule of Assessments. All results, including repeats, will be included in the laboratory reports. The investigator must review the laboratory report, document this review, and record any clinically relevant changes occurring during the trial in the AE section of the eCRF.

3.2.3. Columbia-Suicide Severity Rating Scale (C-SSRS)

Suicidality will be monitored during the trial using the C-SSRS. It was designed to quantify the severity of suicidal ideation and behavior.

This trial will use the "Baseline/Screening" and "Since Last Visit" versions of the scale. The "Baseline/Screening" version, which assesses the lifetime experience of the subject with suicide events and suicidal ideation and the occurrence of suicide events or ideation within a specified time period prior to entry into the trial, will be completed for all subjects at screening to determine eligibility and confirmed at baseline. Any subject with active suicidal ideation or suicidal behaviors within the last 6 months, suicidal behaviors within the last 2 years, or who in the clinical judgment of the investigator presents a serious risk of suicide should be excluded from the trial.

The "Since Last Visit" C-SSRS form will be completed at all visits after screening and baseline. The investigator will review the results of the "Since Last Visit" C-SSRS during the trial to determine whether it is safe for the subject to continue in the trial. If a subject demonstrates potential suicidal ideation associated with actual intent or method or plan as indicated by "YES" answers on item 4 or 5 of the C-SSRS, the investigator will evaluate whether a risk assessment by a qualified mental health professional (or the investigator alone if the investigator is a qualified mental health professional) is needed and whether the subject should continue in or be discontinued from the trial.

Details of C-SSRS categories as well as definition of treatment emerging events are provided in Section 9.4.

3.2.4. Vital Signs

Vital sign measurements will include body temperature, respiratory rate, systolic blood pressure, diastolic blood pressure, and heart rate.

3.2.5. Electrocardiograms

Electrocardiogram recordings will be obtained after the subject has been supine and at rest for at least 5 minutes. Additional 12-lead ECGs may be obtained at the investigator's discretion and should always be obtained in the event of early termination. The ECG results will be evaluated at the investigational site to determine the subject's eligibility and to monitor safety during the trial. The investigator (or qualified designee) will review, sign, and date each ECG reading, noting whether or not any abnormal results are of clinical significance. Any clinically relevant changes occurring during the trial will be recorded in the AE section of the eCRF. The ECG will be repeated if any results are considered to be clinically significant. A central ECG service will be used for reading all ECGs in order to standardize interpretations for the safety analysis.

At screening, triplicate ECG recordings should be taken approximately 1 minute apart. The central ECG service will provide the QT interval corrections based on Fridericia's formula (QTcF) for the 3 screening ECGs. A mean QTcF >450 msec as assessed by the central reader from the screening triplicate ECGs will be exclusionary.

A repeat ECG should be performed to confirm any clinically significant abnormality that is identified in a randomized subject during the treatment period (which will be confirmed by central service read) and, in these cases, the medical monitor should be consulted on the appropriateness of the subject continuing in the trial.

3.2.6. Modified Clinical Institute Withdrawal Assessment – Benzodiazepines

The modified Clinical Institute Withdrawal Assessment – Benzodiazepines (mCIWA-B) is a sensitive instrument to measure withdrawal under conditions where there is a taper of medication (rather than abrupt discontinuation). It consists of 17-items that monitor the type and severity of BZD withdrawal symptoms such as irritability, fatigue, appetite, and sleeplessness (Busto et al, 1989). The clinician-observed assessments of sweating, restlessness (pacing), and tremor that are included in the overall version have been removed from this modified version. The total score ranges from 1 to 68 with higher scores indicating more severe withdrawal.

3.2.7. Concomitant Medications and Non-Drug Therapy/Procedures

Concomitant medications are those medications taken on or after the initiation of IMP. These medications include those medications started before the initiation of IMP and continuing post Day 1. Medications that start and stop before the first dose of IMP will be classified as prior medications and will not be considered concomitant. Medications that start after the last dose of IMP will be classified as taken post last dose and will not be considered concomitant. These medications will be recorded in the eCRF. The investigator will record all medications and therapies (including vaccines, over-the-counter or prescription medicines, vitamins, and/or herbal supplements) that are used by the subject from 30 days before the informed consent form (ICF) is signed through the end of Post-treatment Safety Follow-up Period. The investigator will also

record all medications and therapies taken or received by a subject for treatment of an AE or that cause an AE through the end of Post-treatment Safety Follow-up Period.

Non-drug therapy/procedures will also be recorded as medications described above.

3.2.8. Rescue Medicine

All subjects who normally take BZDs for seizure rescue will be required to have an individualized Rescue Protocol approved by TESC (The Epilepsy Study Consortium). The Rescue Protocol will be submitted along with the SIF/DRF (Seizure Identification and Diagnostic Review Form) and will describe what rescue treatment can be administered in the event the subject requires a BZD. It will also include different scenarios that will prompt immediate medical attention.

3.2.9. Physical and Neurological Examinations

Full physical and neurological examinations should be completed at Screening Visit 4, and Visit 5/ET. The physical examination should include weight at all time points and height at the Screening Visit only.

Any condition present at the post-treatment physical and neurological examinations that was not present at the baseline examination should be documented as an AE and followed to a satisfactory conclusion.

3.3. Pharmacokinetics

To evaluate the plasma exposure of CVL-865 (and adjunctive AEDs, if appropriate) over time, a single daytime blood sample will be collected as specified in the Schedule of Assessments (Section 9.1).

4. DATA CONVENTIONS AND VISIT WINDOWS

4.1. Data Conventions

4.1.1. Age

Age is the age at the time of informed consent and is as captured on the eCRF (note: date of birth is not captured on the eCRF).

4.1.2. Day 1

Day 1 is the day IMP is first initiated.

4.1.3. Study Day of an Event

Study day of an event is defined relative to Day 1 as:

Study $Day = event date - date of Day 1 (+ 1, if event date \ge date of Day 1)$.

This calculation will result in negative study days for an event occurring prior to the start of IMP and positive study days for an event on or after the start of IMP. There will be no Day 0 value to match the schedule of events.

4.1.4. Days on Study

Days on Study is the number of days from Day 1 to the date of study completion or early termination as recorded on the END OF STUDY eCRF.

4.1.5. Days on IMP

Days on IMP is the number of days from Day 1 to the date of last dose of IMP as recorded on the EXPOSURE eCRF.

4.1.6. Baseline Value

For purposes of analysis of safety assessments and efficacy assessments outside of eDiary, the baseline value is defined as the last value obtained prior to initiation of IMP. Should the Day 1 visit value be obtained after the first dose of IMP or if this value is not available at Day 1, then the most recent value obtained prior to earliest initiation of IMP will be used for the baseline value.

4.1.7. Change from Baseline

Change from baseline for a given variable is defined as the value on a given Study Day (Time Point) minus the Baseline Value.

4.1.8. Last Dose of IMP

Last Dose of IMP is defined as the last date that the subject received IMP.

4.1.9. Average Daily Dose by Period

The cumulative dose of IMP, calculated in milligrams and based on the daily dose of IMP as recorded in the EXPOSURE eCRF for each Period defined in Table 3 will be used to derive average daily dose for the period.

4.1.10. Compliance with Study Drug

Dosing compliance, based on daily dose of IMP as recorded in the EXPOSURE eCRF, will be defined by the ratio of the number of doses actually taken by the subject divided by the number of doses that were expected to be taken during the same period multiplied by 100. Subjects could be considered for discontinuation of the trial for non-compliance if poor study drug compliance is observed.

4.1.11. Handling of Incomplete or Missing Dates Associated with an Event

An incomplete date occurs when the exact date an event (e.g. an adverse event) occurred or ended cannot be obtained from a subject. The database contains data fields for month, day, and year. A date is incomplete if at least one of these three fields is not known.

For many of the planned analyses, a complete date is necessary to determine if the event should be included in the analysis (e.g. if the event is treatment-emergent) or to establish the duration of an event. In such cases, incomplete dates will be imputed.

For the purposes of handling partially reported start and stop dates for an event the following algorithm will be applied:

• Missing start day, but month and year present:

If the event occurs same month and year as the occurrence of IMP, then the start day of the event will be assigned to the day of first dose of IMP (i.e., Day 1).

Otherwise the start day will be set to the first day of the month.

• Missing start day and month, but year present:

If event occurs in the same year as IMP, then the start date of the event will be assigned to Day 1.

Otherwise the start day and month will be set to 01 January.

- In the unlikely event of a completely missing start date (year not present), the start date will be imputed as Day 1.
- Missing end day, but month and year present:

The day will be set to the last day of the month.

• Missing end day and month, but year present:

The end day and month will be set to the date of study completion. However, if study completion year is greater than the year of the event, then the day and month will be set to 31 December.

• Missing all components of an end date and the event is not marked as ongoing:

The event will be considered as 'ongoing' and will be considered treatment-emergent if the start date is on or after Day 1.

For completely missing date of epilepsy diagnosis in medical history, the first start date of anti-epilepsy medication(s) will be used to impute the diagnosis date.

If any imputed start date causes the start date to occur after the end date, the end date will be used for the imputation of the start date. If any imputed end date causes the end date to occur prior to the start date of the event, the start date of the event will be used for the imputation of the end date. If the imputed date is later than the date of study withdrawal, then the date of study withdrawal will be imputed for the date. In subject data listings, start and stop date of events will be displayed as reported on the eCRF (i.e., imputed values will not be listed).

4.1.12. Handling of Alphanumeric Data

Should there be instances where a clinical laboratory parameter is reported with imbedded nonnumeric characters, as for example, "<0.1" or ">10", the data will be imputed for quantitative summaries. The actual values as reported in the database will be presented in data listings.

For incorporation in quantitative summaries (except for concentration data), the following imputation rules will be employed:

- The values < LLN will be replaced with ½ the value of the lower limit. For example, "< 0.1" will be replaced with 0.05 if the LLN is 0.1.
- The values > ULN will be replaced by values of increased precision by one level. For example, ">0.1" will be imputed to "0.11", and ">10" will be imputed to "10.1" if the ULN is 10.

4.2. Analysis Periods

The start and end dates of each analysis period (following the study design) are used for the classification of efficacy data. The exact start and end of each of these periods is described for calculation purposes in Section 4.3. Seizure frequency and average daily dose for each analysis period will be calculated based on Table 3.

Table 3:	Definition of Analysis Periods for Seizure Frequency and Average Daily Dose
	Data

Analysis Period	Duration	Start Date	End Date
Baseline Period	~8 Weeks	The greater of: Study Day, -56 or Informed consent	Study Day, -1
Titration Phase	~2 Weeks	Study Day, 1	The lesser of: Day 15 (Visit 2) minus 1 or *Early termination (minus 1) or End of Treatment
Maintenance Phase	~8 Weeks	Day 15 (Visit 2)	The lesser of: **Day 71 (Visit 4) minus 1 or *Early termination (minus 1) or End of Treatment
Taper Phase	~3 Weeks	Day 71 (Visit 4) or *Early termination	End of Treatment

* If a subject experiences early termination from the study and continues to Taper Phase, end dates will be bound by early termination minus 1 while the start of Taper Phase will begin on the date of early termination. ** For subjects continues to Taper Phase from Maintenance Phase

4.3. Visit Windows

Data collected longitudinally across visits will be summarized and analyzed by visit. Visits will be presented according to the nominal study day and visit as obtained from the eCRF or laboratory data unless the visit is an early termination or unscheduled visit. Early termination and unscheduled visits will be assigned visit windows based on the study day completed according to Table 4 -Table 9.

If assessments are collected multiple times within a given visit, the scheduled visit, if available, will be used for summary presentations. If no scheduled visit is available, then the result closest to the scheduled visit date will be used for summary presentations. If two unscheduled measurements (discharge or unscheduled visit) have the same distance to the expected date, the earlier value will be used. If a subject has multiple non-missing unscheduled values on the same date, then the last one is used, as determined by the time collected, if available.

Table 4:Visit Windows for Early Termination and Unscheduled Visits - ECGs and
Vital Signs

Study Day of Early Termination or Unscheduled Visit	Analysis Visit	Analysis Visit Target Day
1 (pre-dose) or earlier	Baseline	
1* to 15	Day 1 (Visit 1)	1
16 to 57	Day 43 (Visit 3)	43
58 to 82	Day 71 (Visit 4)	71
83 to 106	Day 92 (Visit 5)	92
107 and higher	Day 120 (Visit 6)	120

*Only post-dose values at Day 1 will be windowed to Day 1.

Table 5:Visit Windows for Early Termination and Unscheduled Visits - Safety Labs
and C-SSRS

Study Day of Early Termination or Unscheduled Visit	Analysis Visit	Analysis Visit Target Day
1 or earlier	Baseline	
2 to 8	Day 1 (Visit 1)	1
9 to 29	Day 15 (Visit 2)	15
30 to 57	Day 43 (Visit 3)	43
58 to 82	Day 71 (Visit 4)	71
83 to 106	Day 92 (Visit 5)	92
107 and higher	Day 120 (Visit 6)	120

Table 6: Visit Windows for Early Termination and Unscheduled Visits – CGI-S

Study Day of Early Termination or Unscheduled Visit	Analysis Visit	Analysis Visit Target Day
1 or earlier	Baseline	
2 to 8	Day 1 (Visit 1)	1
9 to 29	Day 15 (Visit 2)	15
30 to 57	Day 43 (Visit 3)	43
58 or higher	Day 71 (Visit 4)	71

Table 7:Visit Windows for Early Termination and Unscheduled Visits – PGIC and
CGI-I

Study Day of Early Termination or Unscheduled Visit	Analysis Visit	Analysis Visit Target Day
29 or earlier	Day 15 (Visit 2)	15
30 to 57	Day 43 (Visit 3)	43
58 or higher	Day 71 (Visit 4)	71

Table 8:Visit Windows for Early Termination and Unscheduled Visits – QOLIE-31
and HUI

Study Day of Early Termination or Unscheduled Visit	Analysis Visit	Analysis Visit Target Day
1 or earlier	Baseline	
2 or greater	Day 71 (Visit 4)	71

Table 9:Visit Windows for Early Terminations and Unscheduled – mCIWA-B

Study Day of Early Termination or Unscheduled Visit	Analysis Visit	Analysis Visit Target Day
1 to 74 (on treatment, prior to Taper Phase)	Baseline	
1 to 82 (off treatment)	Day 78 (Contact)	78
83 to 89	Day 85 (Contact)	85
90 to 96	Day 92 (Visit 5)	92
97 to 110	Day 99 (Contact)	99
110 and higher	Day 120 (Visit 6)	120

Cerevel

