5.14.3. Clinical Laboratory Assessments

Descriptive summaries of selected (quantitative) clinical laboratory results will be presented by treatment group and study visit. Laboratory values outside the normal range for each systematically collected hematology, blood chemistry, and urinalysis parameter will be identified. Each subject's hematology, blood chemistry, and quantitative urinalysis values will be flagged as "low" (below the lower limit of normal/LLN), "normal" (within the normal range), or "high" (above the upper limit of normal/ULN) relative to the normal ranges of the central laboratory. Each subject's qualitative urinalysis results will be flagged as "normal" or "abnormal." In addition, the severity of laboratory abnormality will be graded based on toxicity criteria specified in Section 9.6 in reference to Common Terminology Criteria for Adverse

Events (CTCAE) Version 5.0. The result of each laboratory test for individual subjects will be presented in a listing with the normal range defined by the central laboratory, the status relative to the normal range, and the toxicity grade.

Shift table will be used to summarize shifts from baseline toxicity grades to greatest (worst) treatment-emergent laboratory toxicity. For hematology and, blood chemistry, and quantitative urinalysis parameters that toxicity grade was not defined, a shift table for each laboratory test will be based on the shift from baseline high/normal/low status to the status of the maximum post-baseline value and the minimum post-baseline value (including test results from unscheduled visits, if any). Similarly, for qualitative urinalysis parameters, shifts from baseline normal/abnormal status to the worst post-baseline status will be summarized.

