5.14.4. Vital Signs

Vital sign measurements will include body temperature (oral or tympanic), respiratory rate, body weight, systolic blood pressure, diastolic blood pressure, and heart rate. Body temperature, blood pressures, and heart rate will be measured with the subject in a sitting/semi-recumbent position after a 5-minute rest. For the body temperature, the same method must be used for all measurements for each individual subject and should be the same for all subjects at each

investigational site. Vital signs and corresponding changes from baseline will be summarized by visit and treatment group using descriptive statistics.

Number and percent of subjects with out-of-range post-baseline vital signs will be summarized based on the following criteria:

- Systolic Blood Pressure
 - < 90 mmHg,
 - >140 mmHg
- Diastolic Blood Pressure
 - < 50 mmHg
 - > 90 mmHg
- Heart Rate (Supine)
 - < 60 bpm
 - >100 bpm
- Respiratory Rate
 - <12 bpm
 - > 20 bpm
- Temperature
 - $< 36^{\circ} C$
 - $> 38^{\circ} C$

Vital signs results will also be presented as listing with the out-of-range value flagged based on the above criteria.

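### SAP Tables 4 and 5 file early on-drug vital signs and labs under Day 1 (Visit 1), where the by-visit summaries either replace them with the pre-dose value or mislabel them

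*SAP*

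**What the plan says.** SAP 4.3 treats two kinds of visit differently.

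- **Scheduled visits:** "Visits will be presented according to the nominal study day and visit as obtained from the eCRF or laboratory data".
- **ET and unscheduled visits:** "Early termination and unscheduled visits will be assigned visit windows based on the study day completed according to Table 4 -Table 9".

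Table 4 (ECGs and vital signs) has a Baseline row for pre-dose Day 1 or earlier, then a row from Day 1 to Day 15 that maps to Day 1 (Visit 1). The footnote to that row reads "Only post-dose values at Day 1 will be windowed to Day 1". Table 5 (safety labs and C-SSRS) has a Baseline row for Day 1 or earlier, then the row "2 to 8 Day 1 (Visit 1) 1". Table 6 (CGI-S) has the same row.

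The rule for several values in one visit is: "If assessments are collected multiple times within a given visit, the scheduled visit, if available, will be used for summary presentations". SAP 4.1.6 says that "the baseline value is defined as the last value obtained prior to initiation of IMP", and treats a Day 1 value taken after the first dose as an exception.

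The outputs that depend on these slots are in SAP 5.14.4 ("Vital signs and corresponding changes from baseline will be summarized by visit and treatment group using descriptive statistics") and SAP 5.14.3 ("Descriptive summaries of selected (quantitative) clinical laboratory results will be presented by treatment group and study visit"). For ECGs, SAP 5.14.5 has its own rule: several recordings within one time point are averaged.

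**The concern.** Visit 1 is the randomization and first-dispensing visit, so its scheduled vital signs and labs are normally taken before the first dose. Tables 4 and 5 put values from subjects already on drug into a slot with that visit's name. A pre-dose value and an on-drug value can then compete for one cell, and the tie rule favours the scheduled, pre-dose one.

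Subjects with an ET visit during titration plausibly include some who tolerated the drug poorly. If their on-drug values leave the by-visit tables, the early mean changes look milder, and unequally so if early stops differ between arms. Protocol 2.3 names bone marrow suppression and falling peripheral blood counts as important potential risks, so early on-drug labs should be shown correctly.

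**Working it through.** The documents give no figure to reproduce on this point. The check applies the SAP's rules to an ET visit on each day.

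**Inputs**

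- Windows to Day 1 (Visit 1): post-dose Day 1 to Day 15 for vital signs (Table 4); Days 2 to 8 for labs (Table 5).
- Scheduled vital signs at Visits 1, 3, 4 and 5 (Days 1, 43, 71, 92); scheduled labs at Visits 1 to 6 (Days 1, 15, 43, 71, 92, 120), from the Schedule of Assessments.
- Tie rule: the scheduled value is used.

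**Reading A: the scheduled pre-dose value sits at Day 1 (Visit 1) under nominal filing**

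- ET vital signs on any of Days 2 to 15 are displaced by the Visit 1 value.
- ET labs on any of Days 2 to 8 are displaced by the Visit 1 value.

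**Reading B: the scheduled pre-dose value is shown only as Baseline**

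- The same vital signs and labs are kept, but under Day 1 (Visit 1), target day 1.

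**Illustration (invented values).** Systolic pressure is 122 mmHg pre-dose and 84 mmHg at an ET visit on Day 10.

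- Reading A: Visit 1 shows 122, with change 122 − 122 = 0.
- Reading B: Visit 1 shows 84, with change 84 − 122 = −38, labelled Day 1.

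**ECGs.** Table 4 applies to them too, but under SAP 5.14.5 an on-drug ECG placed in the same time point as the pre-dose one would be averaged with it. The on-drug signal is diluted, not replaced.

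**Later windows.** The tie rule also displaces ET labs on Days 16 to 29 (by Visit 2), and ET labs and vital signs on Days 44 to 57 (by Visit 3). There the displacing value is itself on-drug, so the problem is specific to the Visit 1 slot.

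**Window boundaries.** Table 5's cut at Day 8 is the midpoint of Days 1 and 15: (1 + 15)/2 = 8. Table 4's cut at Day 15 is not the midpoint of its adjacent targets, Days 1 and 43: (1 + 43)/2 = 22.

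**Size.** The plan assumes 50 subjects per arm and 20% dropout: 0.20 × 50 = 10 per arm. Assume these are spread evenly over the 10 weeks (70 days) of titration and maintenance, and that each attends an ET visit:

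- Vital signs, about 2 weeks: 10 × 2/10 = 2 per arm.
- Labs, Days 2 to 8 (7 days): 10 × 7/70 = 1 per arm.

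The documents give no rate for unscheduled visits, so those are not counted.

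**Outputs that keep the values as written**

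- Labs: shift tables based on post-baseline extremes, which include unscheduled results, and the hepatic any-occurrence counts (5.14.3).
- Vital signs: counts of subjects with out-of-range post-baseline values (5.14.4). The illustrative 84 mmHg meets the below-90 criterion and is counted.
- ECG: worst post-baseline QTcF (5.14.5).
- C-SSRS: maximum over all post-baseline assessments (5.14.7).
- AE tables and all listings.

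**The case against.** The strongest reply is that nothing need be lost. Tables 4 and 5 list Baseline and Day 1 (Visit 1) as separate slots, the Table 4 footnote reserves Day 1 for post-dose values, and 4.1.6 makes the last pre-dose value Baseline. On that view the on-drug value survives and only its label is loose. This stands as a legitimate reading, so loss cannot be stated as certain. It does not clear the plan: nominal-visit filing equally permits the other reading, nothing chooses between them, and calling a Day 10 value Day 1 is still wrong.

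Several stronger inferences are tempting but not supported:

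- **That the ET value is the subject's only on-drug vital-sign record.** The Schedule of Assessments has early terminators begin the taper, and Visit 5, in the Taper Phase, includes vital signs. The documents do not say clearly whether such subjects also attend Visit 5.
- **That many subjects are affected.** Assuming 5 to 15% of an arm stops in titration gives 2.5 to 7.5 of 50. The upper end is 7.5/10 = 75% of all planned dropout in the first 2 of 10 weeks.
- **That the out-of-range vital-sign table is affected.** It is described by post-baseline values, with no reference to windowed visits.
- **That Table 7 contradicts Table 5** by sending a Day 6 PGIC or CGI-I to Visit 2. Neither scale is collected at Visit 1, so Table 7 has no Visit 1 slot to use.

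It is also fair to object to moving Day 2 labs into Visit 2: that exchanges one wrong label for another, 15 − 2 = 13 days off.

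**Conclusion.** The point holds as a defect in the windowing rules with a small, bounded effect. Either on-drug vital signs and labs are displaced by a pre-dose value, or they are shown under the wrong day; the SAP leaves the choice open and neither result is right. ECGs sharing the time point would be blended with the pre-dose recording.

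The effect reaches only by-visit descriptive safety summaries, for about 1 to 2 subjects per arm. That figure rests on evenly spread dropout and ET attendance; early stopping concentrated in titration would raise it. The conclusion also rests on scheduled Visit 1 values being pre-dose, which the SAP implies through 4.1.6 and the Baseline row of Table 4 but does not state outright. A reader might infer that early safety signals would be hidden altogether. The documents do not support that, because the worst-value, shift, out-of-range, AE and listing outputs retain these records as written.

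**What to change.** 1. Add to SAP 4.3 that a scheduled Visit 1 value taken before the first dose is Baseline only, and that it neither displaces nor is averaged with a post-dose record.
2. In Tables 4 and 5, replace the post-dose row mapped to Day 1 (Visit 1) with a separate post-baseline row, for example 'Titration Phase (ET/unscheduled)', keeping the present day ranges. Change the identical row in Table 6 for consistency. Table 3 starts the Maintenance Phase on Day 15, so word the new Table 4 row to suit a Day 15 value.

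The cost is SAP wording and a change to the window lookup before database lock. No new data are needed. The downside is an extra table row with a small n, to be read descriptively.
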